12.3 Investigator Assessment of Adverse Events

If a diagnosis is clinically evident (or subsequently determined), the diagnosis rather than the individual signs and symptoms or lab abnormalities will be recorded as the AE.

All solicited (see Table 9 below) and unsolicited AEs will be recorded through 7 days after each vaccination, including injection site reactions, or until resolved. After that period, only unsolicited AEs (including symptomatic malaria), SAEs, UPs, and NOCIs will be recorded. Note that a positive BS without associated clinical symptoms (i.e., asymptomatic parasitemia) will not be reported as an AE. Clinical or symptomatic malaria will be reported as an AE.

Table 9. Solicited Adverse Events

Systemic adverse events
Fever (temperature ≥38.0 °C)
Headache
Nausea/Vomiting
Diarrhea
Abdominal pain
Fatigue
Malaise
Myalgia
Arthralgia
Urticaria
Local reactogenicity
Injection pain/tenderness
Injection erythema/redness
Injection swelling
Injection induration
Injection pruritus
Limitation of arm movement
Limitation of arm movement

Abbreviations: ALT, alanine transaminase; ANC, absolute neutrophil count; AGC, absolute granulocyte count; CR, creatinine; WBC, white blood cell.

Additional laboratory abnormalities other than those specified as safety labs in the protocol should be reported as AEs if they require intervention. Interventions include, but are not limited to, discontinuation of treatment, dose reduction/delay, additional assessments, or concomitant treatment. In addition, any medically important laboratory abnormality may be reported as an AE at the discretion of the investigator. This could include a laboratory result for which there is no intervention, but the abnormal value suggests a disease or organ toxicity. In addition, , all laboratory AEs will be collected and graded through 14 days after the first and second vaccination and 28 days after the third vaccination or until resolved.

The investigator will assess all AEs with respect to seriousness (criteria listed above), severity (intensity or grade), and causality (relationship to study agent and relationship to research) according to the following guidelines.

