12.3.2 Causality

Causality (likelihood that the event is caused by the study agent(s)) will be assessed considering the factors listed under the following categories:

Definitely Related

- reasonable temporal relationship
- follows a known response pattern
- clear evidence to suggest a causal relationship
- there is no alternative etiology

Probably Related

- reasonable temporal relationship
- follows a suspected response pattern (based on similar agents)
- no evidence of a more likely alternative etiology

Possibly Related

- reasonable temporal relationship
- little evidence for a more likely alternative etiology

Unlikely Related

• does not have a reasonable temporal relationship

OR

• good evidence for a more likely alternative etiology

Not Related

- does not have a temporal relationship OR
- definitely due to an alternative etiology

Note: Other factors should also be considered for each causality category when appropriate. Causality assessment is based on available information at the time of the assessment of the AE. The investigator may revise the causality assessment as additional information becomes available.

The degree of certainty with which an AE can be attributed to administration of the study vaccine will be determined by how well the event can be understood in terms of one or more of the following:

- The event being temporally related with vaccination or reproduced on re-vaccination.
- A reaction of similar nature having previously been observed with this type of vaccine and/or formulation.
- The event having been reported in the literature for similar types of vaccines.
- Whether or not there is another identifiable cause.

All local (injection site) reactions will be considered causally related to vaccination. All malaria cases will be reported as not related to vaccination.

Reports will further classify AEs as follows:

Related - all AEs that are assessed as definitely, probably, or possibly related. Unrelated - all AEs assessed as unlikely or definitely not related.

Causality assessment will be provided by the Principal Investigator or designee and reviewed by the sponsor. The sponsor may make a separate and final determination on the "reasonable possibility" that the event was "related" or "unrelated" to the study agent, in keeping with applicable (US FDA) guidance on sponsor IND safety reporting.

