15.4.1 Study Vaccines

15.4.1.1 IM Vaccinations

Possible local vaccine reactions resulting from IM injection include pain, swelling, erythema, induration, limitation of limb movement for several days, lymphadenopathy, or pruritus at the injection site. Systemic reactions such as fever, chills, headache, fatigue, malaise, myalgia, and joint pain may also occur, and may range from mild to severe. These side effects will be monitored but are generally mild and self-limiting.

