15.4.1.5 Matrix-M

Common solicited AEs during past administrations of other vaccines containing the adjuvant Matrix-M (including the COVID Vaccine candidate, NVX-CoV2373) are: injection site pain, redness, induration, and swelling and the following systemic AEs: fever, nausea/vomiting, headache, fatigue, malaise, myalgia and arthralgia.

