15.4.1.7 Verorab Rabies Vaccine

The following adverse reactions have been associated with Verorab Rabies Vaccine:

Very common (≥ 1/10): adenopathy/lymphadenopathy; myalgia; injection-site pain; fever; malaise.

Common (\geq 1/100): cutaneous allergic reactions such as rash, pruritus, and oedema; headache; dizziness; abdominal pain; nausea; somnolence; arthralgia; shivering; injection-site erythema, pruritus, hematoma, and induration; asthenia; influenza-like syndrome.

Uncommon ($\geq 1/1000$): injection-site swelling; urticaria; angioedema; dyspnea; diarrhea.

Verorab Rabies Vaccine is considered a Category B vaccine. One animal toxicity study on reproduction and development led with another inactivated rabies vaccine produced in VERO cells, did not evidence any deleterious effect on female fertility and on pre- and post-natal development. Clinical use of rabies vaccines (inactivated "WISTAR Rabies PM/WI38 1503-3M strain") during a limited number of pregnancies did not show any malformative or fetotoxic effects to date.

For complete safety details, please refer to the package insert provided for Verorab Rabies Vaccine.

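### Table 9 does not solicit lymphadenopathy, chills/shivering or injection-site bruising, which the protocol lists as reactions or grades elsewhere, so every arm relies on unsolicited reporting for them

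*Combined protocol and SAP*

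**What the plan says.** **Recording (12.3).** The rule is "All solicited (see Table 9 below) and unsolicited AEs will be recorded through 7 days after each vaccination, including injection site reactions". Beyond that window, "After that period, only unsolicited AEs (including symptomatic malaria), SAEs, UPs, and NOCIs will be recorded". Table 9 has ten systemic terms and six distinct local terms. None of them is lymphadenopathy, chills or shivering, or bruising.

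**Reactions named elsewhere.** Section 15.4.1.1 covers IM vaccination in general, so it applies to every arm. Its local list includes "limitation of limb movement for several days, lymphadenopathy, or pruritus", and its systemic list includes chills. For the rabies vaccine, section 15.4.1.7 gives as very common "adenopathy/lymphadenopathy; myalgia; injection-site pain; fever; malaise". Its common band includes "headache; dizziness; abdominal pain; nausea; somnolence; arthralgia; shivering; injection-site erythema, pruritus, hematoma, and induration; asthenia; influenza-like syndrome".

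**Grading and causality.** Appendix B has a row for bruising at the site but none for lymphadenopathy or chills, which therefore fall to the generic definitions in Table 10. Section 12.3.2 says "All local (injection site) reactions will be considered causally related to vaccination". It does not say whether a swollen axillary node counts as local.

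**Analysis (14.1, 14.2).** The plan applies Fisher's exact test to AE proportions, compares the proportion of subjects with at least one AE, and may compare the number and severity of AEs. Line listings sort each event as local, solicited or other.

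**The concern.** Reactions asked about by name are generally recorded more completely than those a participant has to volunteer. The primary objective of this first-in-human trial is safety and reactogenicity against rabies vaccine. The solicited list nevertheless omits two reactions that the protocol's own risk section attributes to the injections, and a third that its toxicity table is ready to grade. No reason is given.

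Section 3.5 makes the nodal omission more notable, because it describes Matrix-M as raising the number of activated immune cells in the draining lymph nodes. A nodal reaction is therefore of interest in the vaccine arms as well as the control arm. Prompted answers for the days after each dose cannot be recovered once the visits are over.

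**Working it through.** **1. The plan's own figures.** Section 14.1 gives the chance of seeing at least one event, which is 1 − (1 − p)^n.

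| n | p | Stated | Recomputed |
|---|---|---|---|
| 20 | 0.077 | 0.80 | 0.799 |
| 20 | 0.109 | 0.90 | 0.901 |
| 60 | 0.026 | 0.80 | 0.794 |
| 60 | 0.037 | 0.90 | 0.896 |

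These reproduce. The point disputes no stated figure.

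**2. Table 9 against the protocol's other lists.**

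| Source | Terms | In Table 9 | Not in Table 9 |
|---|---|---|---|
| 15.4.1.1, any IM injection | 14 (7 local, 7 systemic) | 12 | lymphadenopathy, chills |
| 15.4.1.7, very common | 5 | 4 | lymphadenopathy |
| 15.4.1.7, common | 14 | 7 (8 if asthenia is read as fatigue) | cutaneous allergic reactions, dizziness, somnolence, shivering, site hematoma, influenza-like syndrome (and asthenia) |
| 15.4.1.5, Matrix-M | 11 | 11 | none |

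**3. What the visits require.** Section 12.2 asks for appropriate questioning and examination at each contact. The Appendix A instructions for 1, 3 and 7 days after each dose (Days 2, 4, 8; 30, 32, 36; 58, 60, 64) call for a focused examination that names the injection site and acute complaints. They do not name the axilla, so these instructions do not require checking the nodes of someone without complaints.

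**4. Expected lymphadenopathy in controls.** Taking the 10% floor from 15.4.1.7 as the rate, 20 × 0.10 = 2.0 cases are expected, and P(at least 1) = 1 − 0.90^20 = 0.878. The share captured without prompting is not in the documents, so a range is assumed.

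| Share captured | Cases recorded | P(at least 1 recorded) |
|---|---|---|
| 25% | 0.5 | 0.397 |
| 50% | 1.0 | 0.642 |
| 75% | 1.5 | 0.790 |
| 100% | 2.0 | 0.878 |

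**5. Largest effect on the proportion of controls with at least one AE.** Assume independence, a common rate r for the other four very common reactions, and no lymphadenopathy captured. The proportion without lymphadenopathy is 1 − (1 − r)^4, and the loss is (1 − r)^4 × 0.10.

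| r | Without | With | Loss | Of 20 controls |
|---|---|---|---|---|
| 10% | 34.4% | 41.0% | 6.6 points | 1.3 |
| 20% | 59.0% | 63.1% | 4.1 points | 0.8 |
| 30% | 76.0% | 78.4% | 2.4 points | 0.5 |

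With 50% captured, each loss halves, to about 1.2 to 3.3 points, or less than one control participant.

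**6. Lymphadenopathy tested alone.** The power of Fisher's exact test (two-sided 0.05 assumed), with 10% in controls and an extreme 0% in vaccinees, is 0.04 for 20 v 20 and 0.32 for 20 v 60. If only half is captured, so that 5% is recorded, it is 0.003 and 0.075.

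**The case against.** The strongest reply is that nothing is lost by design. Unsolicited AEs are recorded, the primary endpoint covers all local and systemic AEs, every contact includes questioning and examination, and the same form is used in all arms under double blinding. The case report form is not in the documents and may prompt for more than Table 9 does. This stands as a limit on the size of the problem. It does not explain why Table 9 departs from 15.4.1.1 and Appendix B. Nor does the at-least-one-AE comparison cover everything: the number, the severity and individual proportions of AEs may also be compared, and there a missed event can matter even in someone who has another AE.

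A reader might go further and infer that control-arm harms are under-elicited, because Table 9 covers 11 of 11 Matrix-M reactions but not all the comparator's. Floor frequencies could be used to size this. Verorab's listed reactions sum to 5 × 0.10 + 14 × 0.01 = 0.64 per participant, of which 0.10 + 6 × 0.01 = 0.16 are unsolicited (asthenia read as fatigue). At 50% capture that is 0.16 × 0.5 / 0.64, an under-count of about 12%. The documents do not support this, for four reasons:

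- Section 15.4.1.5, with "injection site pain, redness, induration, and swelling and the following systemic AEs: fever, nausea/vomiting" among its terms, describes AEs that were solicited in past trials. Finding them all on a solicited list is close to circular. Matrix-M is also only the adjuvant.
- Four Table 9 terms (diarrhea, abdominal pain, urticaria, injection pruritus) are on the comparator's list and not on the Matrix-M list, so Table 9 is not tailored to Matrix-M.
- Sections 15.4.1.1 and 3.5 make nodal reactions plausible in the vaccine arms. If they are more frequent with rabies vaccine, missing them makes the study vaccine look relatively worse. If they are more frequent with Matrix-M, missing them hides a vaccine harm. If the rates are similar, there is little bias.
- The 12% sums overlapping terms, treats minimum frequencies as rates, assumes a capture share and assumes no loss in the vaccine arms.

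**Conclusion.** The omission is real and applies to all arms. Lymphadenopathy, chills/shivering and injection-site bruising are not solicited, although 15.4.1.1, 15.4.1.7 and Appendix B between them treat all three as reactions to expect or to grade. Their capture depends on unsolicited reporting.

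The consequence is modest: 2 expected lymphadenopathy cases in 20 controls at the label floor, and at most about 2 to 7 points on the control proportion with at least one AE. Those figures rest on the floor being the true rate, on independence, on assumed rates of 10% to 30% for the other very common reactions and, for the upper end, on no unprompted capture. That prompting improves capture is general experience and is not quantified in the documents. No direction of bias between arms can be concluded. This is a worthwhile, inexpensive improvement to data collection and does not invalidate the primary comparison.

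**What to change.** Add injected-side axillary lymphadenopathy, chills/shivering and injection-site bruising to Table 9 and to the forms used over the 7 days after each dose, identically in all arms. Check for them within the focused examinations already scheduled.

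Reconcile Table 9 with 15.4.1.1, 15.4.1.7 and Appendix B, or explain any omission that is kept. State how lymphadenopathy and chills are graded, and whether a nodal reaction counts as local under 12.3.2. That last question should be settled deliberately. Automatic relatedness for nodal reactions is not recommended here, because relatedness feeds the pausing and halting criteria.

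The cost is three extra form lines at existing visits, a short amendment, and slightly higher solicited AE counts in every arm. Sections 12.8.1 and 12.9 already count related Grade 3 events whether solicited or not, so fuller capture could still raise those counts. The sponsor should check that effect before adopting the change.

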12.3.1 Severity

Severity of AEs will be assessed by the investigator according to the toxicity tables provided in Appendix B. AEs not included in the Appendices will be graded for severity using the definitions provided in Table 10.

Table 10. Definitions for Severity of AE Grading

Severity	Definition
Grade 1 (Mild)	No interference with activity, may use 1 dose
	of an over-the-counter medication
Grade 2 (Moderate)	Repeated use of non-narcotic pain reliever
	>24 hours or some interference with activity
Grade 3 (Severe)	Activities of daily living limited to <50% of
	baseline, medical evaluation/therapy required
Grade 4 (Potentially Life-Threatening)	Extreme limitation in activity, significant
	assistance required; immediate medical
	intervention or therapy required to prevent
	death
Grade 5	Death

12.3.2 Causality

Causality (likelihood that the event is caused by the study agent(s)) will be assessed considering the factors listed under the following categories:

Definitely Related

- reasonable temporal relationship
- follows a known response pattern
- clear evidence to suggest a causal relationship
- there is no alternative etiology

Probably Related

- reasonable temporal relationship
- follows a suspected response pattern (based on similar agents)
- no evidence of a more likely alternative etiology

Possibly Related

- reasonable temporal relationship
- little evidence for a more likely alternative etiology

Unlikely Related

• does not have a reasonable temporal relationship

OR

• good evidence for a more likely alternative etiology

Not Related

- does not have a temporal relationship OR
- definitely due to an alternative etiology

Note: Other factors should also be considered for each causality category when appropriate. Causality assessment is based on available information at the time of the assessment of the AE. The investigator may revise the causality assessment as additional information becomes available.

The degree of certainty with which an AE can be attributed to administration of the study vaccine will be determined by how well the event can be understood in terms of one or more of the following:

- The event being temporally related with vaccination or reproduced on re-vaccination.
- A reaction of similar nature having previously been observed with this type of vaccine and/or formulation.
- The event having been reported in the literature for similar types of vaccines.
- Whether or not there is another identifiable cause.

All local (injection site) reactions will be considered causally related to vaccination. All malaria cases will be reported as not related to vaccination.

Reports will further classify AEs as follows:

Related - all AEs that are assessed as definitely, probably, or possibly related. Unrelated - all AEs assessed as unlikely or definitely not related.

Causality assessment will be provided by the Principal Investigator or designee and reviewed by the sponsor. The sponsor may make a separate and final determination on the "reasonable possibility" that the event was "related" or "unrelated" to the study agent, in keeping with applicable (US FDA) guidance on sponsor IND safety reporting.

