3.2.1 Safety of Pfs230D1M-EPA/AS01 in Healthy Adults

Pilot Phase

In the pilot phase of the study, there was a staggered dose escalation of Pfs230D1M and Pfs25M, given individually and in combination. In the Pfs230D1M arms alone, vaccinations with the low dose of Pfs230D1M (13 μ g) and high dose of Pfs230D1M (40 μ g) were overall well-tolerated. Most of the related AEs were mild (Grade 1; 13 μ g: 23/29, 79%; 40 μ g: 42/51, 82%), with the majority being injection site pain. Laboratory abnormalities were also observed, with the majority being transient, asymptomatic Grade 1 (mild) and Grade 2 (moderate) neutropenias. As the high dose (40 μ g) of the Pfs230D1M/AS01 was determined safe and tolerable in the pilot study, it was selected to be used for the main phase of the study.

Main Phase

In the main phase of the trial, there was a full-dose arm (n=56) and a fractional-dose arm (n=61). The full-dose arm received Pfs230D1M-EPA/AS01 at 40 μg at 0, 1, 6, and 18 months. The fractional-dose arm received Pfs230D1M-EPA/AS01 at 40 μg at 0, 1, and 18 months and received a fractional dose of 8 μg of Pfs230D1M-EPA/AS01 at dose #3 at 6 months. Because there is no fractional dosing in the proposed trial, full details of the fractional dosing arm are not provided here; overall, the AE profile was similar to that of the full-dose arm, and further details can be found in the Investigator Brochure.

First 3 vaccinations: In the full-dose arm (n=56), the first three vaccinations were well tolerated with 66% (252/383) of the total AEs being mild. The most common Grade 1 AEs were injection site pain (95/252; 38%) followed by headache and malaria. Of the related Grade 2 AEs, 16/24 (67%) were injection site pain. Other related Grade 2 AEs were 2 episodes each of fever, headache, arthralgias, and neutropenia. Grade 1 injection site pain was reported in the full-dose arm in 95/168 (57%) doses, fractional-dose arm in 78/180 (43%) doses and control arm in 39/360 (11%) doses. Grade 2 injection site pain was also significantly greater in the full-dose and fractional-dose arms compared to the control. Grade 1 headaches were significantly greater in the full-dose arm than the control arm.

Booster dose: The fourth dose of Pfs230D1M-EPA/AS01 was well tolerated; most AEs were mild (Grade 1 AEs; 160/363, 44%). The most commonly reported Grade 1 AE was injection site

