9.4.1.1 Symptomatic Malaria

Clinical or symptomatic malaria for this study is defined as the presence of asexual P. falciparum parasites at any parasitemia with at least one of the following symptoms: temperature of ≥ 37.5 °C and/or one or more of the following symptoms: headache, myalgia, arthralgia, malaise, nausea, dizziness, or abdominal pain.

For clinical diagnostics, RDTs will be utilized for determination of an acute malarial illness. The RDT will be paired with collection and reading of a thick BS.

Participants diagnosed with malaria will be treated with either AL or another approved/licensed anti-malarial medication per Malian Government treatment guidelines.

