12.9 Halting Rules for the Protocol

Halting the study requires immediate discontinuation of study agent administered for all subjects and suspension of enrollment until a decision is made whether or not to continue enrollment and study agent administration.

The following criteria will be used to define unacceptable reactogenicity of the malaria vaccine (AEs that are possibly, probably, or definitely related to the vaccine will be considered "related" and will be summarized as such):

- 1 or more subject(s) experience an SAE as defined in Section 12.1 of this protocol that is determined to be possibly, probably, or definitely related to the vaccine, **or**
- 1 or more subjects experience a hypersensitivity reaction (e.g. anaphylaxis, diffuse urticaria) that is determined to be possibly, probably, or definitely related to the vaccine, or
- Pilot Group: > 20% (2 or more of n=5) of vaccinees assigned to an experimental vaccine dosage (either low, middle or high dose) experience any Grade 3 AE (solicited or unsolicited) lasting 48 hours or more or any Grade 3 laboratory abnormality with either the AE or lab abnormality determined to be possibly, probably, or definitely related to the vaccine as defined in this protocol, within the 7 days post vaccination
- Main Group*: ≥20% (4 or more of n=20) of vaccinees assigned to an experimental vaccine dosage (either low, middle or high dose) experience any Grade 3 AE (solicited or unsolicited) with signs or symptoms lasting for 48 hours or more or any Grade 3 laboratory abnormality with either the AE or lab abnormality determined to be possibly, probably, or definitely related to the vaccine as defined in this protocol, within the 7 days post vaccination

or

• Any safety issue that the study PI or CSO determines should halt the study.

*Once the Main Group starts, Halting Rules will be based on review of data from all 20 participants receiving a specific experimental vaccine dosage (n=20)

If halting criteria are met based on blinded data, the list of research participants with the Grade 3 AEs or laboratories will be sent to the DSMB Executive Secretary. A DSMB Meeting could be convened on short notice at the occurrence of such an event.

In addition, the FDA, FMPOS EC and/or CSO may halt the study at any time.

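### The malaria coding rules permit a solicited systemic symptom within 7 days of a dose to be recorded as malaria, and so as unrelated, and the text does not say which recording instruction governs

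*Combined protocol and SAP*

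**What the plan says.** Five places in the protocol bear on this point.

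- **Section 9.4.1.1** defines clinical malaria as the "presence of asexual P. falciparum parasites at any parasitemia with at least one of the following symptoms": a temperature of 37.5 °C or more, headache, myalgia, arthralgia, malaise, nausea, dizziness or abdominal pain. There is no density cut-off and no exception for the days after a dose. On testing it says "RDTs will be utilized for determination of an acute malarial illness", paired with a thick smear.
- **Section 12.3** says that, where a diagnosis is clinically evident, "the diagnosis rather than the individual signs and symptoms or lab abnormalities will be recorded as the AE". Parasitaemia without symptoms is not an AE; symptomatic malaria is, and is named among the unsolicited events. The same section says "All solicited (see Table 9 below) and unsolicited AEs will be recorded through 7 days after each vaccination" and has the investigator assess every AE for causality.
- **Section 12.3.2** fixes the causality of malaria: "All malaria cases will be reported as not related to vaccination". It also lets the sponsor make its own final determination.
- **Section 12.9** counts a Grade 3 AE lasting at least 48 hours towards the percentage halting rules only if it is "possibly, probably, or definitely related to the vaccine as defined in this protocol, within the 7 days post vaccination". The thresholds are 2 of 5 per dose in the Pilot Group and 4 of 20 per dose once the Main Group starts.
- **Section 12.8.1** pauses dosing of one participant for a single Grade 3 or worse event lasting 72 hours or more, with the same limits of relatedness and 7 days.

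**The concern.** Because parasitaemia alone is not an AE, in a carrier a vaccine-caused headache or fever can be the very thing that turns a non-event into a malaria case. Causality is then settled by rule rather than judged, even when the timing and the known reaction pattern point to the vaccine. The symptoms exposed to this are the ones expected of the product.

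At stake are the relatedness part of the primary safety summary (Section 14.2) and two formal safety rules in a first-in-human escalation. With five vaccinees per pilot dose, one recoded event can decide whether the halting threshold is reached. For the individual pause, one recoded event is enough to leave that participant's next dose not automatically suspended.

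**Working it through.** The plan gives no figure for this point. Its nearest figures, the binomial safety power in Section 14.1, reproduce from 1 − (1 − p)^n: 0.799 and 0.901 for n = 20 at p = 0.077 and 0.109; 0.794 and 0.896 for n = 60 at p = 0.026 and 0.037 (stated 0.80 and 0.90 for each n).

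**1. Overlap of symptoms**

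- Table 9 has 10 systemic events. Seven meet the malaria list: fever, headache, nausea, abdominal pain, malaise, myalgia, arthralgia. Diarrhea, fatigue and urticaria do not. Every solicited fever (38.0 °C or more) passes the 37.5 °C cut-off.
- Section 15.4.1.5 lists the common Matrix-M systemic events as fever, nausea/vomiting, "headache, fatigue, malaise, myalgia and arthralgia". Six of these seven overlap (all but fatigue).
- Section 3.2.1, AS01 full-dose arm: of 24 related Grade 2 AEs, 16 were injection-site pain. "Other related Grade 2 AEs were 2 episodes each of fever, headache, arthralgias, and neutropenia" accounts for the other 8. The six clinical systemic ones all overlap, giving 6/24 = 25%.

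**2. Timing**

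Accrual is September to October 2021 (Synopsis), and the third dose is on Day 57, 56 days after Day 1. Nominal third doses therefore run from 27 October (first dose 1 September) to 26 December (first dose 31 October). All doses fall nominally within the June to December season given in Section 6.1.

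**3. Effect on the halting rules**

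Let p be the true rate of qualifying related Grade 3 events per vaccinee, s the share that are overlapping systemic symptoms, and L the chance that such an event is recoded (carriage × chance of being tested and recoded). The counted rate is r = p(1 − sL). The halting probability is P(X ≥ 2 | 5, r) in the pilot and P(X ≥ 4 | 20, r) in the main stage.

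None of these inputs is in the documents for this trial. I assume s = 0.25 (the Grade 2 share above, carried over to Grade 3) and L from 1% (for example 2% × 0.5) to 15% (30% × 0.5).

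| p | L | r | Pilot, 2 of 5 | Main, 4 of 20 |
|---|---|---|---|---|
| 10% | 0 | 0.1000 | 8.1% | 13.3% |
| 10% | 1% | 0.09975 | 8.1% | 13.2% |
| 10% | 5% | 0.09875 | 8.0% | 12.9% |
| 10% | 15% | 0.09625 | 7.6% | 12.0% |
| 20% | 0 | 0.2000 | 26.3% | 58.9% |
| 20% | 1% | 0.1995 | 26.2% | 58.6% |
| 20% | 5% | 0.1975 | 25.8% | 57.8% |
| 20% | 15% | 0.1925 | 24.7% | 55.5% |

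At L = 5% the largest change is 58.9% to 57.8%.

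**4. An arm exactly at its threshold**

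If all the qualifying events are overlapping ones, the chance that at least one is recoded and the rule is missed is 1 − (1 − L)^2 in the pilot and 1 − (1 − L)^4 in the main stage. For L = 1%, 5% and 15% this is 2.0%, 9.8% and 27.8% (pilot) and 3.9%, 18.5% and 47.8% (main).

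These are conditional on an uncommon state. With p = 10%, L = 1% and every event overlapping, the joint probability is 0.0729 × 0.0199 = 0.15% (pilot) and 0.0898 × 0.0394 = 0.35% (main).

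**5. The individual pause**

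One overlapping event suffices, so the chance of missing the pause, given such an event, is L itself.

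**The case against.** The strongest reply is that Section 12.3 can be read the other way. All solicited events are recorded for 7 days, all AEs are assessed for causality, and symptomatic malaria is classed as unsolicited. On that reading the headache stays a solicited AE with its own causality and malaria is entered alongside it, so nothing is lost. This is a natural reading, but the section also has the diagnosis replace its symptoms and does not reconcile the two. What stands is an ambiguity that permits the loss, and a reader should not infer that the plan definitely removes these reactions.

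A reader might also infer that the halting rules are seriously weakened. The documents do not support that. Applying recoding to every qualifying event (s = 1) at L = 5% would move the main-stage figure at p = 20% from 58.9% to 54.4%. But local reactions, fatigue, diarrhea and urticaria cannot meet the malaria definition, and a laboratory abnormality alone cannot either. Carriage is not given, and Section 6.1 describes Sotuba's inoculation rates as historically much lower than at the other sites. Related Grade 3 events have been uncommon: none after the AS01 booster (Section 3.2.1).

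Safeguards also remain. The malaria event stays in the all-AE comparisons against randomised controls (Sections 14.1 and 14.2). The DSMB reviews trial safety data before the Main Group starts (Section 1.2.1), the ISM reviews safety, the sponsor may reassess causality, and the PI or CSO may halt for any safety issue. Section 7.5 lets an investigator defer a dose when a condition could cloud safety interpretation. Several of these are discretionary, and none automatically restores a recoded event to the count. The DSMB review follows the first 40-µg injections; Section 1.2.1 shows none between the pilot dose steps.

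Finally, an investigator assessing a febrile participant with a positive test may still judge the symptom unlikely related. That is so, but it would then be a judgement on the case.

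**Conclusion.** The concern holds as an unresolved conflict in the text. The rules permit a solicited systemic symptom in a carrier to be coded as unrelated malaria, and so to leave the related-AE summary, the halting counts and the pausing rule. They do not say whether the 7-day recording instruction prevents this.

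The likely effect on the probability of halting is small: about 1 percentage point or less under the assumptions s = 25% and L = 5%, and up to about 3.4 points at L = 15% (main stage, p = 20%). The true frequency cannot be determined from the documents. The practical weight lies in the pilot arms, where a single event can settle 2 of 5, and in the individual pause. A text change is worth making because it is cheap and closes a gap in a first-in-human safety rule, not because a large distortion is expected.

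**What to change.** Add to Sections 12.3 and 12.3.2, with a cross-reference from 12.8.1 and 12.9:

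> Solicited symptoms that start within 7 days of any vaccination are recorded, graded and individually assessed for causality as solicited AEs, whatever the smear or RDT result. Malaria, if diagnosed, is recorded as an additional AE. The automatic not-related classification applies to the malaria diagnosis only, and not to these symptoms when the rules in Sections 12.8.1 and 12.9 are applied.

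This needs no new visits or tests, since the symptoms are already solicited and malaria testing is already in place. It has two costs. One illness may appear as more than one AE. Some true malaria symptoms may be judged related, so a pause or halt may trigger more readily.

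For a deliberately pessimistic bound on the second cost, suppose 1% to 5% of vaccinees (assumed, q) had true Grade 3 malaria symptoms lasting 48 hours or more within 7 days of a dose, all judged related.

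- With no other qualifying event, the halting chance per dose arm is P(X ≥ 2 | 5, q) = 0.1% to 2.3% (pilot) and P(X ≥ 4 | 20, q) = under 0.1% to 1.6% (main).
- On top of a 10% rate of other qualifying events, the combined rate is 1 − 0.9(1 − q) = 10.9% to 14.5%. The pilot figure rises from 8.1% to between 9.5% and 15.6%, and the main figure from 13.3% to between 16.7% and 32.8%.

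The real cost should be lower, because Section 12.3.2 lets the investigator class a symptom as unlikely related when there is good evidence of another cause. Any excess falls on the side of caution.
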